### **6.2 Secondary Endpoints**

Quantitative analysis of perfusion abnormalities in correlation with clinical MRI results. This will be achieved by quantitative analysis, identifying regions of interest and generating time intensity curves.

### **6.3 Statistical Methods**

#### **6.3.1 Baseline Data**

Baseline and demographic characteristics will be summarized by standard descriptive summaries.

### **6.3.2 Safety Analysis**

All subjects entered into the study and receiving at least one injection of investigational drug will be included in the safety analysis. The frequencies of AEs by type, severity, and temporal relationship to the CEUS scan will be summarized. SAEs (if any) will be described in detail.

Adverse events will be recorded at 1) 60 minutes post-scanning when the monitoring period is completed, and 2) through 48 hours post-scanning, with documentation at 48 hours post-scanning if no adverse event presents until this point.

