#### **3.1.2 Study Treatment Phase**

Investigational CEUS scan will be performed separately from clinically indicated conventional US, in the ICU. CEUS will be performed at the time HII is first suspected or diagnosed. A second CEUS may be performed at short-term follow-up (approximately within 1-2 weeks from the first scan) for a total of two CEUS exams of 1 hour and 20-minute duration each.

Injection of Lumason™ contrast agent will be performed via the existing peripheral intravenous line or central line using the FDA-recommended dose of up to 0.03 mg/kg. Contrast-agent injection will be performed twice per CEUS scan to ensure image quality and test reproducibility. In the case of more stable patients without an IV line, a peripheral IV line will be started to conduct the investigational CEUS. Two bolus

injections will be performed to evaluate for dynamic brain perfusion and several 2-minute cine clips as well as static images will be acquired during the exam.

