### Adverse event assessment and documentation

Adverse events will be recorded at 1) 60 minutes post-scanning when the monitoring period is completed, and 2) through 48 hours post-scanning, with documentation at 48 hours post-scanning if no adverse event presents until this point. During the 48-hour AE assessment period, the following AEs of special interest will also be assessed:

- a. worsening cardiopulmonary status,
- b. worsening pulmonary hypertension, which may be suggested by new requirement of nitric oxide use, elevated pulmonary artery pressures on echocardiography, or differential limb pulse oximetry measurements,
- c. worsening neurological status, and
- d. serious gastrointestinal complications

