##### **4.5.1 Early Termination Study Visit**

A subject may be withdrawn by a parent prior to or during a CEUS scan, provided the 60 minute monitoring is completed after injection of the investigational drug. The CEUS examination will be terminated if there is a deterioration in the subject's clinical status during imaging.

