Risks of the administration of the study drug are considered a minor increase above minimal risk, without the prospect of direct benefit. Adverse effects are not dose-dependent, thus risk is not increased by modifying the timing of interventions or increasing the number of contrast-agent injections.

Another risk of the study includes the insertion of a peripheral IV line. This is a no greater than minimal risk procedure, with the main risks of discomfort, bruising, and infection which are generally self-limited. There is a no greater than minimal risk of breach of confidentiality, which is minimized by having all of study personnel undergo HIPAA training.

Interference of CEUS with MRI is not expected since CEUS contrast-agent Lumason clears within minutes after injection. Elimination of Lumason (Sulfur Hexafluoride Lipid-Type A Microspheres) occurs via the lungs in the first minutes following contrast-agent injection (please see Package Insert's section 12.3 Pharmacokinetics for more detail, attached in Application's section 12.02 (3.0)). Additionally, [name], the sponsor-investigator, has also previously performed brain CEUS before MRI in neonatal patients without adverse events.

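### The safety table leaves out any infant who has a research-only IV line placed or attempted but is never injected

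*Combined protocol and SAP*

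**What the plan says.** Section 6.3.2 gives the only safety population in the plan: "All subjects entered into the study and receiving at least one injection of investigational drug will be included in the safety analysis". The synopsis repeats it under both Safety Evaluations and Statistical And Analytic Plan. The planned summary is: "The frequencies of AEs by type, severity, and temporal relationship to the CEUS scan will be summarized". The recording schedule is also tied to the scan: "Adverse events will be recorded at 1) 60 minutes post-scanning when the monitoring period is completed, and 2) through 48 hours post-scanning". The same two time points recur in Section 4.2 (adverse event assessment), 8.1, 8.3 and 9.4.1 (steps to minimize risks), and the exam checklists in 4.2.1 and 4.2.2 follow the same clock.

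On the line, Section 3.1.2 states: "In the case of more stable patients without an IV line, a peripheral IV line will be started to conduct the investigational CEUS". Section 9.4.1 then says: "Another risk of the study includes the insertion of a peripheral IV line". It grades this as no more than minimal risk, "with the main risks of discomfort, bruising, and infection which are generally self-limited". Section 4.5.1 provides for stopping before any drug is given: "A subject may be withdrawn by a parent prior to or during a CEUS scan".

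**The concern.** For some infants the study involves two exposures: a line inserted only for research, and the contrast agent. The safety population is defined by the second exposure alone. An infant who has the first without the second, because access failed or because the family withdrew after placement, drops out of the table by definition, even though the protocol itself counts the first exposure as a study risk.

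Section 9.4.2 says that participants receive no direct benefit. In that setting the account of harm should cover everything done to the infant for research, including minor events. A reader of the final safety table would not learn that such infants existed or what happened to them.

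**Working it through.** The plan states no figure that could be reproduced here. The check is a comparison of sections, followed by an illustration of scale.

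**Step 1. Follow an infant with a research line and no injection through the plan.**

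| Question | Source | Answer |
|---|---|---|
| Exposed to a study procedure? | 3.1.2 | Yes, the line is started for the research scan |
| Is it a listed study risk? | 9.4.1 | Yes |
| Can the infant leave before injection? | 4.5.1 | Yes, withdrawal before a scan is allowed |
| Does a harm meet the AE definition? | 8.3 | Yes, interventions other than drugs count |
| Can it be recorded? | 8.1, 8.3 | Yes: AEs are followed for the whole study and all go on the case report form |
| Is there a scheduled recording point? | 4.2, 6.3.2, 8.1, 8.3 | No, both points are counted from the scan |
| Can it be classified by timing relative to the scan? | 6.3.2 | No, there was no scan |
| Is the infant in the safety analysis? | 6.3.2, synopsis | No |

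The exclusion in the last row is certain from the text. The recording gap is partial: the broad wording allows capture, but no scheduled prompt ensures it.

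**Step 2. The optional second exam.** An infant injected at CEUS #1 is in the safety set. If a research line fails at CEUS #2, one to two weeks later, the 48-hour window of the first scan has closed and no second window opens. The event could be tabulated if recorded, but again no scheduled point covers it.

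**Step 3. Scale, on assumptions only.** Section 3.4 projects 200 enrolled and 100 evaluable. The gap is 200 − 100 = 100, and the plan does not say how many of those are never injected or how many had a line attempted. Let m be the number with a research line placed or attempted and no injection.

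- Assume 10% need a research line and 5% of those are not injected: 200 × 0.10 × 0.05 = 1.
- Assume 30% and 10%: 200 × 0.30 × 0.10 = 6.

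With an assumed line-harm rate p per infant, the chance that at least one harm is missing from the table is 1 − (1 − p)^m, and the safety set is at most 200 − m.

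| m | Safety set at most | p = 1% | p = 5% |
|---|---|---|---|
| 0 | 200 | 0% | 0% |
| 1 | 199 | 1.0% | 5.0% |
| 6 | 194 | 5.9% | 26.5% |
| 20 | 180 | 18.2% | 64.2% |
| 50 | 150 | 39.5% | 92.3% |

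The rows for 20 and 50 are stress values. The documents support no particular value of m or p.

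**The case against.** The strongest reply is that an injected-only set is a common and defensible choice for a drug study under an IND, and that the protocol has other ways to notice a line complication. Section 8.2 sends unanticipated problems related to the research to the IRB. Section 8.8 calls a temporary halt for any serious event, whether or not the drug caused it. Section 4.5 documents whether each subject completes. Serious line harms would therefore reach oversight, and what could go untabulated is mainly the minor harm that Section 9.4.1 describes. All of this stands, and it limits the importance of the point. It does not bring a non-injected infant into the safety analysis.

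Three stronger readings are tempting, and the documents do not support them.

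- A reader might infer that these events go unrecorded. Sections 8.1 and 8.3 are wide enough to cover them, and the 48-hour point sets an end to collection without fixing a start.
- A reader might infer that all research-line harms are lost. Infants who are injected stay in the safety set, and nothing in 6.3.2 bars events before the scan.
- A reader might infer that complications cluster in the omitted infants. That is plausible when access fails, but no section says so. The protocol never describes a failed placement, and 4.5.1 does not say that a line would already be in place at withdrawal.

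Failed access also bears on the feasibility aim in Section 6, but it is not an endpoint, so that argument adds little.

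**Conclusion.** The point holds as a matter of definition: the safety table omits infants who undergo research line placement, or an attempt at it, and receive no injection. The plan also gives no scheduled AE time point for an infant who is not scanned. It does not follow that the reported harm will be understated, only that it could be. The number affected is unknown, may be zero and is probably small: 1 to 6 of 200 under the assumed rates above. The harms concerned are mostly minor on the protocol's own description. This is a low-cost improvement to the completeness of harm reporting and does not threaten the study's conclusions.

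**What to change.** In Section 6.3.2 and the synopsis:

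- Keep the injected set for drug-related adverse events.
- Add a second set of all infants who undergo any research procedure, including an attempted peripheral line placement.
- State that AE collection starts at the first research procedure of each exam. Define its end for infants not scanned, for example 48 hours after the last research procedure.
- Tabulate line-related events separately from events after injection.
- Record on the case report form whether a line was placed or attempted solely for research, so that the second set can be identified.

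The scan-based timing appears in 4.2, 4.2.1, 4.2.2, 6.3.2, 8.1, 8.3 and 9.4.1. All of these need the same wording, or the protocol will contradict itself. The cost is one small additional table, one data item and minor text edits. No clinical procedure changes.

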## **6.4 Sample Size and Power**

Power analyses indicate that the study is sufficiently powered to detect group perfusion differences. For example, given a basal ganglia PE mean value in the control group of 1.37 (SD = 0.23) and in the patient group of 0.96 (0.09), with an alpha p = 0.05, power to detect group differences with a sample of 25 per group approaches 1.00. As another example, given a peak cortical perfusion mean value in the control group of 2.46 (SD = 1.96) and in the patient group of 0.69 (0.20), with an alpha p = 0.05, power to detect group differences with a sample of 50 per group approaches 0.84.

Given a sample of about 100 imaged patients, pilot data suggest that approximately one-half will show abnormal perfusion, thus providing a final sample of approximately 50 patients with abnormal perfusion and 50 patients with normal perfusion. The above sample sizes were used to compute the power to detect group differences in the ratio of basal ganglia to cortex perfusion, using means and standard deviations obtained from the pilot sample (see Preliminary Data).

Power analyses indicate that the study is sufficiently powered to detect group perfusion differences. For example, given a basal ganglia PE mean value in the control group of 1.37 (SD = 0.23) and in the patient group of 0.96 (0.09), with an alpha p = 0.05, power to detect group differences with a sample of 50 per group approaches 1.00. As another example, given a peak cortical perfusion mean value in the control group of 2.46 (SD = 1.96) and in the patient group of 0.69 (0.20), with an alpha p = 0.05, power to detect group differences with a sample of 50 per group approaches 0.85.

An interim statistical analysis may be considered to review image quality and comparisons between the results of each subject's CEUS scans and available clinical US exams, to better inform the number of subjects required for statistical significance.

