### **6 STATISTICAL CONSIDERATIONS**

Up to 100 evaluable patients should be adequate for assessment of clinical feasibility and optimization of protocol. Qualitative analysis will be used as detailed above. Quantitative analysis will be performed by drawing a region of interest in brain segments and compared to control subjects (those with suspected or at risk of HII but turns out to be normal on imaging and clinical evaluation) using non-parametric Wilcoxon testing.

The study will optimize current techniques in the application of contrast ultrasound. For instance in brain imaging, the optimal plane in which to obtain the contrast perfusion kinetics curve is suggested but not established. The region of interest placement for perfusion kinetics quantification is also suggested by few publications, but not established as the standard practice. All this is part of the optimization process that is pivotal to improving the current contrast ultrasound techniques.

Specific analysis plan consists of both qualitative and quantitative assessment in which description of focal perfusion deficit or lesion, for instance, is reported in correlation with clinical information. Perfusion abnormalities will be qualitatively evaluated (absent – 0, mild hypoperfusion – 1, normal – 2, hyperperfusion – 3) and quantitatively (region of interest placed on brain regions for acquisition of wash-in curves using QLab or Qontrast or other similar software). These abnormalities will be correlated to MRI findings as gold standard, non-contrast ultrasound, and clinical information (neurologic exam, hemodynamics, behavioral outcomes) between serial exams. For extremely injured brain cases, nuclear scan (for diagnosis of brain death) instead of MRI may be performed as part of gold standard

The sample size will be based on the available cases, and based on the current number of patients presenting to Children's Hospital of Philadelphia neonatal or pediatric intensive care unit with clinical suspicion for hypoxic ischemic injury. It is estimated that the study will achieve a sample size of up to 50 neonates and infants per year for up to two years.

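### Section 6.4 gives power of 0.84 and then 0.85 for peak cortical perfusion from identical inputs at 50 per group; those inputs give more than 0.99

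*Combined protocol and SAP*

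**What the plan says.** Section 6.4 contains two near-identical paragraphs of power examples. Each gives the cortical inputs in the same words, "given a peak cortical perfusion mean value in the control group of 2.46 (SD = 1.96) and in the patient group of 0.69 (0.20"), and sets alpha at 0.05. The first paragraph concludes "power to detect group differences with a sample of 50 per group approaches 0.84". The second concludes "power to detect group differences with a sample of 50 per group approaches 0.85".

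The companion basal ganglia example (controls 1.37, SD 0.23; patients 0.96, SD 0.09) also appears twice. In the first paragraph it reads "power to detect group differences with a sample of 25 per group approaches 1.00"; in the second the same power is stated for 50 per group.

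Between the two, the section explains that about 100 imaged patients should split into about 50 with abnormal and 50 with normal perfusion. It then says "The above sample sizes were used to compute the power to detect group differences in the ratio of basal ganglia to cortex perfusion". The values entered are attributed to earlier pilot work and not to any published source.

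Section 6 states that "The sample size will be based on the available cases" and that the quantitative comparison with control subjects will be made "using non-parametric Wilcoxon testing". Section 6.4 names neither the test behind the power figures nor whether alpha is one-sided or two-sided.

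**The concern.** One set of inputs cannot give two powers. The gap of 0.01 is trivial in itself, but it prompts a recalculation, and both figures then prove to be far below what the inputs give.

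A gap that large is not rounding or choice of software. At least one printed number is wrong: a mean, an SD, the group size or the power. If it is the power, the comparison is much better powered than the section says. If it is a mean or an SD, the effect size that the section relies on is unknown.

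Two features make the inputs harder to trace. The basal ganglia group size changes from 25 to 50 between the paragraphs. The section also says that power was computed for a ratio of basal ganglia to cortex perfusion, whereas this example is labelled as peak cortical perfusion. The section contemplates an interim analysis to inform the number of subjects, and that would need a sound starting effect size and SD.

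**Working it through.** **Inputs (Section 6.4).** Control mean 2.46, SD 1.96; patient mean 0.69, SD 0.20; alpha 0.05; 50 per group. Two-sided testing is assumed, since sidedness is not stated; a one-sided test would only raise power. The Wilcoxon test comes from Section 6.

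**Effect size.**
- Difference: 2.46 − 0.69 = 1.77.
- Root-mean-square SD: √[(1.96² + 0.20²)/2] = √[(3.8416 + 0.0400)/2] = √1.9408 = 1.393.
- Standardised difference: d = 1.77/1.393 = 1.27.

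**Attempt to reproduce 0.84/0.85 at 50 per group.** The noncentrality is d·√(n/2) = 1.2705 × √25 = 6.35. With 98 degrees of freedom the two-sided critical value is 1.984, far below 6.35.

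| Method, 50 per group, two-sided 0.05 | Power |
|---|---|
| Pooled t (98 df) | 0.99999 |
| Welch t (50.0 df) | 0.99999 |
| Simulated Wilcoxon, normal data | 0.9995 to 0.9999 across simulation runs |
| Simulated Wilcoxon, lognormal or gamma data | 1.00 |
| SD 1.96 in both groups, t (d = 1.77/1.96 = 0.903, noncentrality 4.515) | 0.994 |
| SD 1.96 in both groups, simulated Wilcoxon | 0.992 |

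The stated figures are not reproduced by any of these.

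**What 0.84 to 0.85 would require at 50 per group (pooled t).**
- d of 0.597 (power 0.84) to 0.605 (power 0.85), against 1.27 stated.
- With the SDs as printed, a difference of 0.597 × 1.393 = 0.83 to 0.605 × 1.393 = 0.84, against 1.77.
- With the means as printed, a common SD of about 1.77/0.597 = 2.96 to 1.77/0.605 = 2.93; or, keeping the patient SD at 0.20, a control SD of about 4.19 to 4.13, against 1.96.

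**Other readings tried.**
- *Uneven split of 100 (controls/patients, Welch):* 40/60 gives 0.9998, 30/70 gives 0.998, 20/80 gives 0.97, 15/85 gives 0.90 and 12/88 gives 0.81. Only a split between the last two would reach 0.84 to 0.85, and the section states 50 and 50.
- *25 per group, SDs as printed:* pooled t 0.993, Welch 0.991, Wilcoxon on normal data 0.97.
- *Smaller groups, SDs as printed:* about 12 per group gives 0.845 (pooled t).
- *25 per group with SD 1.96 in both groups:* t 0.88 (noncentrality 3.193), simulated Wilcoxon about 0.85. This comes close, but it needs both the group size and one SD to be misprinted, and nothing in the text confirms it.

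**Control check: basal ganglia.** The difference is 1.37 − 0.96 = 0.41 and the root-mean-square SD is √[(0.23² + 0.09²)/2] = 0.175, so d = 2.35. Power is about 1.00 at 25 and at 50 per group. That example reproduces at both sizes, so the same method recovers the section's other figure.

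**The case against.** The strongest reply is that nothing turns on the figure. The size was set by the cases available and justified by feasibility, and the power statements are offered as examples. The quantitative comparison is also a secondary endpoint: the primary endpoint is the qualitative reading against MRI. On the printed inputs, correction makes the claim of sufficient power stronger. All of this stands, and it limits the weight of the point. It does not make the figure right, and it does not cover the case where a mean or SD is what was misprinted.

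Second, the change from 25 to 50 per group in the basal ganglia example is not an arithmetic error, since power is about 1.00 at either size. That is correct; it is a matter of tidying the text.

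Third, the pilot values may be set out in preliminary results or figures missing from the text available here. That is possible. The source of the inputs and the ratio-versus-peak labelling might be settled there. The mismatch between the printed inputs and the printed power would remain.

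Fourth, means and SDs alone do not fix the power of a Wilcoxon test. True: the Wilcoxon figures hold for the distributions simulated. They agree closely across normal, lognormal and gamma shapes, and with the t-based results.

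**Conclusion.** The concern holds. Section 6.4 states two powers, 0.84 and 0.85, for one set of inputs, and neither follows from them. At 50 per group and two-sided alpha 0.05, power is above 0.999 with the printed SDs and 0.992 to 0.994 with the larger SD in both groups. This rests on the printed means, SDs and equal groups; for the Wilcoxon test it also rests on the distributions simulated. Sidedness does not affect the conclusion.

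The direction is an understatement of power, so this is not evidence that 50 per group is too few. It shows that a printed number is wrong, and the text reviewed does not identify which. Until that is settled, 0.84 or 0.85 should not be cited in support of 50 per group. The point should be fixed, but it does not threaten the design.

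**What to change.** 1. Check the cortical means, SDs and group size against the pilot data, and establish whether the measure is peak cortical perfusion or a ratio of basal ganglia to cortex. Label it accordingly.
2. Keep one of the two duplicated paragraphs, with one group size for the basal ganglia example.
3. Name the test and the sidedness, and restate cortical power once for the planned two-sided Wilcoxon test. If the printed inputs are confirmed, that is above 0.99 at 50 per group, with the distributional assumption stated. If not, recompute from the corrected inputs.
4. Optionally, add that 50 per group gives about 85% power for a difference of about 0.6 SD (t test), which does not depend on the pilot estimates.

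The cost is a look at the pilot data and a few lines in Section 6.4. Nothing changes in the conduct of the study.

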### **2.1 Primary Objective (or Aim)**

The primary objective is to identify regions of interest in gray versus white matter to detect the ratio of perfusion changes, in cases of diffuse white matter ischemia.

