### **6.1 Primary Endpoint**

Qualitative analysis of perfusion abnormalities in correlation with clinical MRI results.

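### The primary objective has no matching endpoint, analysis or power, and Section 6.4 forms its two groups differently from Section 6

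*Combined protocol and SAP*

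**What the plan says.** **Objective and endpoints.** Section 2.1, repeated in the abstract and synopsis, sets the primary objective: "identify regions of interest in gray versus white matter to detect the ratio of perfusion changes, in cases of diffuse white matter ischemia". Section 6.1 gives the primary endpoint: "Qualitative analysis of perfusion abnormalities in correlation with clinical MRI results". Section 6.2 is the quantitative counterpart, also against MRI, and adds: "This will be achieved by quantitative analysis, identifying regions of interest and generating time intensity curves".

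**Groups.** Section 6 plans a Wilcoxon comparison in which region-of-interest values are "compared to control subjects (those with suspected or at risk of HII but turns out to be normal on imaging and clinical evaluation"). It names no modality there. For the separate correlation analysis it says: "These abnormalities will be correlated to MRI findings as gold standard", and it allows a nuclear scan in place of MRI for the most severely injured brains. Section 6.4 starts from about 100 imaged infants and expects that "approximately one-half will show abnormal perfusion, thus providing a final sample of approximately 50 patients with abnormal perfusion and 50 patients with normal perfusion".

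**Size and power.** Section 6 says: "Up to 100 evaluable patients should be adequate for assessment of clinical feasibility and optimization of protocol". Section 6.4 says that the group sizes were "used to compute the power to detect group differences in the ratio of basal ganglia to cortex perfusion" and gives two examples at alpha 0.05. Basal ganglia PE (control 1.37, SD 0.23; patient 0.96, SD 0.09) has power near 1.00 at 25 and at 50 per group. Peak cortical perfusion (control 2.46, SD 1.96; patient 0.69, SD 0.20) has 0.84 in the first paragraph and 0.85 in the third, both at 50 per group.

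**The concern.** Two things do not fit together.

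1. The study could complete its primary endpoint analysis and still not answer its primary objective. A four-level visual reading compared with MRI does not yield a gray:white ratio. No power or precision is stated for the ratio or for the reading, so a reader cannot tell how well 100 infants would answer either question.

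2. Sorting infants by perfusion is not the same as sorting them by imaging and clinical status. The outcome of the Wilcoxon test is CEUS perfusion. If a CEUS reading helps decide who is a control, some of the difference found between groups is created by the sorting. A small p-value would then be weaker evidence that hypoxic ischemic injury (HII) changes perfusion.

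**Working it through.** **1. Objective, endpoint and power side by side**

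| Element | Quantity | Gray:white ratio? | Power or precision given? |
|---|---|---|---|
| 2.1 primary objective | gray versus white matter ratio | yes | no |
| 6.1 primary endpoint | qualitative reading against MRI | no | no |
| 6.2 secondary endpoint | regions of interest, time-intensity curves, against MRI | not named | no |
| 6.4 power | basal ganglia PE, peak cortical perfusion, basal ganglia to cortex ratio | no | yes |

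Basal ganglia and cortex are both gray matter, so 6.4 contains no white-matter term. The tools that the primary objective needs appear only under the secondary endpoint.

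**2. The plan's own power figures**

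Normal approximation, two-sided alpha 0.05: power = Φ(δ / (s√(2/n)) − 1.96), with s² the mean of the two variances.

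- Head-count: 100 × 1/2 = 50 per group. Reproduces.
- Basal ganglia PE: δ = 1.37 − 0.96 = 0.41; s = √((0.23² + 0.09²)/2) = 0.175. At n = 25, δ/(s√(2/25)) = 8.30, so power is effectively 1.00. It is also 1.00 at n = 50. Reproduces.
- Peak cortical perfusion: δ = 2.46 − 0.69 = 1.77; s = √((1.96² + 0.20²)/2) = 1.393. At n = 50, δ/(s√(2/50)) = 6.35, so power exceeds 0.999. With the larger control SD in both groups (s = 1.96) the ratio is 4.52 and power is 0.995. A simulated Wilcoxon test on normal data gives 0.999. **The printed 0.84 and 0.85 do not reproduce**, and identical inputs carry two different values. Power of 0.84 to 0.85 would correspond to about 11 to 13 per group, or 22 to 23 with the control SD in both groups.

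Unequal groups change little. With 100 infants in total, Welch power for the cortical example is 0.998 with 30 controls, 0.97 with 20 and 0.90 with 15.

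**3. What happens if CEUS influences the labels**

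All inputs here are assumptions; the documents give none. There are 100 infants. The perfusion measurement x is N(0,1) with no true HII effect. The CEUS reading is v = r·x + √(1 − r²)·e, with e an independent N(0,1) error and r = 0.5. Each infant has a 40% chance of being HII by MRI or clinical status, unrelated to x. An infant is a control only if neither HII by that status nor abnormal on CEUS. The test is a two-sided Mann-Whitney on x at 5%, with 20,000 trials per row.

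| Abnormal on CEUS | Rejection rate |
|---|---|
| CEUS not used | 5% |
| 5% low | 9% |
| 10% low | 17% |
| 20% low | 37% |
| 15% low, 5% high | 12% |
| 10% low, 10% high | 5% |

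The rate depends on how many infants CEUS moves and in which direction. It also depends on r: in the 20%-low row it is 16% at r = 0.3 and 64% at r = 0.7.

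**4. Precision for 6.1, as an illustration**

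Section 1.1 cites sensitivity 88.9% and specificity 66.6% from a 12-neonate study. Assume 50 MRI-positive and 50 MRI-negative infants: 0.889 × 50 ≈ 44 and 0.666 × 50 ≈ 33. The exact (Clopper-Pearson) 95% limits are the 2.5% quantile of Beta(x, n − x + 1) and the 97.5% quantile of Beta(x + 1, n − x).

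- 44/50: 0.76 to 0.95
- 33/50: 0.51 to 0.79

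**The case against.** The strongest reply on grouping is that the abnormal/normal sentence in 6.4 is only a forecast of yield from pilot data. The power examples speak of control and patient groups, which fits Section 6, and Section 6 requires a normal clinical evaluation as well as normal imaging. MRI is called the gold standard, Section 4.2 describes a clinical MRI as standard of care, and Section 5 bars CEUS from directing care without confirmation. The pilot groups may also be defined in material not visible here. Much of this stands. A reader might infer that CEUS sets the groups and that a false-positive result is close to certain. The documents do not support that: no section gives CEUS that role, the clinical requirement argues against CEUS acting alone, and the rating scale includes increased as well as decreased flow, which can cancel the bias. What remains is that none of these statements governs group assignment, and the two sections describe the groups differently.

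A second reply is that the power claim is limited by its own wording to group perfusion differences, and that Section 6 justifies 100 infants on feasibility. Both are true. A reader might infer that the plan claims power for its primary endpoint, or that it is underpowered; neither follows. The gap is a missing justification, not a false statement. The McNemar comparison of grayscale with contrast ultrasound and the optional interim analysis do not fill it, because neither gives precision for CEUS against MRI.

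Nothing in the documents answers the mismatch between 2.1 and 6.1/6.2.

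**Conclusion.** The point holds in two parts of different strength.

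The mismatch is certain on the text: the primary objective has no endpoint, analysis or power of its own, and the primary endpoint has no stated precision.

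The grouping problem is an inconsistency with an open risk. If study CEUS is kept out of the labels there is no inflation. If it enters, the rate is about 5% to 37% in the cases with correlation 0.5 and 40% HII, and no document figure fixes those inputs. The size of 100 evaluable infants is not in dispute, and power for the quantitative comparison is adequate on 6.4's inputs. Separately, the cortical power figures of 0.84 and 0.85 are wrong for their stated inputs. They understate power, so correcting them does not weaken the plan. This should be fixed before analysis.

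**What to change.** - **Section 6:** assign HII and control status from MRI, or the nuclear-scan alternative already stated, plus clinical evaluation. State that no study CEUS result is used. Report separately the infants with neither scan and those whose scan and clinical status disagree.
- **Section 6.4:** use the same groups in place of the abnormal/normal perfusion split. Correct 0.84 and 0.85 for the cortical example at 50 per group, or give the inputs that produce them. The conclusion that power is adequate does not change.
- **Sections 2.1, 6.1, 6.2 and the synopsis:** reconcile them so that the primary objective has a matching endpoint and analysis. Which one is primary is the sponsor's choice. Name the summary measure for it and give its expected precision; if 6.1 stays primary, the intervals above show the form.

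**Cost:** no new data; wording, two corrected numbers, a short precision statement and one sponsor decision. The downsides are that a less favourable precision figure will stand beside power near 1.00, and that some infants without a reference scan cannot be placed in a group.
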